6.3.2 Blinding

The study will be conducted with a double blind. Because L9LS has a slight yellow tint, and the placebo (normal saline) is colorless, the pharmacy team will cover all syringes with transparent yellow tape to maintain blinding. The subjects, the clinical staff, and the study team will be blinded to study treatment allocation, with the exception of designated individuals who administer the study agents and remain separate from the team of blinded investigators who conduct all subsequent follow-up study assessments. The pharmacy team at the study site where administration is taking place will be unblinded, and they are responsible for maintaining security of study treatment assignments.

Data will remain blinded until the last subject completes the final study visit. Subjects will then be informed about their study treatment assignment.

Unscheduled unblinding, either intentional (e.g., in the case of a medical emergency in a subject) or unintentional, will be handled according to SOPs. Intentional and unintentional unscheduled unblinding will be documented in the appropriate source and/or research record and will include the reason for the unscheduled unblinding, the date it occurred, who approved the unblinding, who was unblinded, who was notified of the unblinding, and the plan for the subject.

The principal investigator will report all cases of intentional and unintentional unscheduled unblinding to the DSMB in writing within 1 business day after site awareness via email to the DSMB mailbox ([contact]) outlining the reason for the unblinding and the date it occurred. The report will also be submitted to the EC and the SMM.

If an SAE or other event merits unblinded review for safety (i.e., per the principal investigator, regulatory authority, or the SMM), the unblinding occurrence and a summary of how unblinded review and assessment was conducted for safety (preferably by the DSMB), will be summarized in the SAE or regulatory safety report. However, the actual treatment assignment will not be disclosed unless the particular participant is being globally unblinded per study leadership and sponsor.

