8.2.3 Correlative Studies for Research/Pharmacokinetic Studies

The following evaluations will be performed according to the schedule presented in section 1.3.

Blood smear: Thick blood smears will be prepared and analyzed by the standard WHO method (section 2.2.3) to identify Pf infection for the primary endpoint. This evaluation will be performed centrally in the laboratory in Bamako, unless the subject is displaying signs or symptoms of clinical malaria, in which case the blood smear will be analyzed at the time of the scheduled or unscheduled visit.

Pf RT-PCR: RT-PCR will be performed to identify Pf infection as a secondary endpoint. This evaluation will be performed at the University of Washington on coded dried blood spots.

PK studies: Blood L9LS concentrations will be measured by Meso Scale Discovery LLC-based automation platform. The concentration at the visit prior to the first Pf infection will be used to assess L9LS-mediated protection. This evaluation will be performed at the NIAID.

ADA detection: Assays for detection of ADA will be performed at specified timepoints (section 1.3) following product administration and compared to baseline status. This evaluation will be performed at the NIAID.

Parasite genotyping: For subjects who become infected during the study, coded blood samples collected around the time of the first infection will be used to perform a genotypic sieve analysis to analyze sequences of breakthrough parasites (section 9.4.11). This evaluation will be performed by [name] at the Harvard School of Public Health.

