9.4.4 Efficacy Analyses

Incidence of malaria infection is primarily defined as blood smear–positive Pf infection through 24 weeks after administration, and secondarily as determined by RT-PCR. The efficacy analyses will be MITT.

The primary efficacy analysis will be based on time to the first infection. The survival patterns will be described by Kaplan-Meier curves for each arm. The protective efficacy of the study product will be assessed from the Cox proportional hazards model with study arm as the only regressor and estimated by one minus the hazard ratio. This will be achieved via R package “straweib” that accounts for interval censoring. To address the heterogeneity of the study population, as a sensitivity analysis, a Cox regression with regressors other than the study arm will be additionally performed to account for potential differences among participants. The regressors will include time of enrollment and possibly those covariates that are significantly different between the study product arm and the placebo arm in spite of randomization.

The secondary efficacy analysis will be based on the proportion of subjects who become infected during the 24-week follow-up period. The proportion of subjects who become infected during the 24-week follow-up period will be estimated for each arm and compared across arms based on Kaplan-Meier estimates along with 95% confidence intervals via R package “bpcp.” This estimation accounts for right censoring and the comparison should be equivalent to Fisher’s exact test in case of no censoring. Though not accounting for interval censoring, the Kaplan-Meier estimates are appropriate as the interest is on infection at 24 weeks only.

Protective efficacy of L9LS will be primarily assessed over all participants by comparing all L9LS recipients with placebo recipients. As a secondary objective, the protective efficacy of L9LS will also be assessed among female participants by comparing female recipients of L9LS with female placebo recipients; and a stratified analysis by weight will also be performed. An exploratory analysis will be conducted to assess how the weight-based dosage, in terms of mg of L9LS per kg of subject body weight, affects the protective efficacy. No multiplicity adjustment will be applied to the secondary and exploratory analyses.

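### The blind may end at the last subject's final visit, before the last smears are read, late adverse-event judgements are settled or the database is locked

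*Combined protocol and SAP*

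**What the plan says.** Section 6.3.2 states the rule in two sentences: "Data will remain blinded until the last subject completes the final study visit. Subjects will then be informed about their study treatment assignment". On who is blinded, it says "The subjects, the clinical staff, and the study team will be blinded to study treatment allocation", apart from the designated people who give the injections; the pharmacy team is also unblinded. Laboratory smear readers are not named separately.

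Section 9.4.4 defines the efficacy endpoint as smear-positive "Pf infection through 24 weeks after administration, and secondarily as determined by RT-PCR". The schedule in Section 1.3 takes a smear and a dried blood spot on day 168, the last scheduled visit. Section 8.2.3 says of smear reading: "This evaluation will be performed centrally in the laboratory in Bamako, unless the subject is displaying signs or symptoms of clinical malaria". In subjects with symptoms the smear is read when they attend. Of RT-PCR it says: "This evaluation will be performed at the University of Washington on coded dried blood spots". No deadline is given for either.

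On adverse events, Section 8.4.2.3.1 sets a minimum entry frequency with a lag. Section 8.4.2.1.2 lets the investigator revise causality and lets the sponsor make a separate final determination. Section 8.4.2.3.2 continues follow-up of unresolved serious events beyond the planned period.

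**The concern.** The trigger is a clinic visit, whereas blinding is meant to protect the results and judgements derived from the visits. Some of these come later. The primary efficacy endpoint is read by people at a microscope (Section 2.2.2.3), and Section 9.4.5 compares related adverse events between arms, so both depend on judgement.

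Once subjects know their arm, site and laboratory staff in Mali could learn it too. The documents do not say that they would, and they contain no safeguard against it. A smear read, or a causality grade revised, after that point would no longer be protected by the blind. Even if nothing went wrong, the trial could not show from its own protocol that every endpoint reading was made blind.

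**Working it through.** The main check is a comparison of the release rule with the sections that govern when each kind of result becomes final. Sample size, power and alpha do not depend on the date of unblinding, so there is no figure in the plan to reproduce.

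1. **Conditions for release.** Section 6.3.2 names the last subject's final visit and nothing else. Elsewhere in the document there is no data freeze, no database lock and no requirement that readings be complete. Section 10.3 speaks of locking only for records and freezers.

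2. **Smears.** The endpoint runs through week 24 and the last smear is taken on day 168. A subject without symptoms has it read in Bamako, away from the visit. So when the last subject leaves that visit, that subject's smear is unread unless symptoms led to a reading on the spot. The same can hold for others who finished shortly before. How many is unknown, because no turnaround time is given.

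3. **Which of those smears matter.** The primary analysis uses time to first infection. A subject already positive has an event that the day-168 smear cannot change. For a subject negative through day 154, the day-168 reading decides between an event in the interval from day 154 to day 168 and censoring.

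   An illustrative ceiling can be set, assuming that the 78.2% placebo infection rate cited in Section 4.1 applies here and that efficacy is 0.6 to 0.8, as in Table 4:
   - Placebo uninfected at 24 weeks: 72 × (1 − 0.782) = 15.7, about 16.
   - L9LS infection rate: 0.782 × 0.4 = 0.313 at efficacy 0.6, and 0.782 × 0.2 = 0.156 at efficacy 0.8.
   - L9LS uninfected: 216 × (1 − 0.313) = about 148, to 216 × (1 − 0.156) = about 182.

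   These counts show who would still be negative. They do not count exposed readings, since only late finishers whose smear is unread at the trigger are exposed. Earlier infection narrows the exposure sharply in the placebo arm. In the L9LS arm the narrowing comes mainly from finishing date.

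4. **RT-PCR.** The last subject's day-168 result must be open at the trigger, because the spot still has to reach an outside laboratory. That laboratory receives coded spots, the sample-code key stays in Bamako (Section 2.2.2), and the randomization lists are held by the pharmacist (Section 6.3.1). Telling subjects in Mali their arm does not by itself tell the laboratory.

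5. **Adverse events.** Entry is at least every 2 weeks and covers data up to 1 week before entry. An event just after one cut-off can therefore wait up to about 2 + 1 = 3 weeks. An event close to the last visit can still be unentered at the trigger, although serious events have faster reporting. Causality revision has no cut-off and no requirement that it be done blind.

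6. **Primary safety endpoint.** It covers 7 days after dosing. For any subject that window closes 168 − 7 = 161 days (23 weeks) before the nominal final visit, so only late or reopened judgements and queries remain.

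7. **Which visit is final.** Appendix C also calls the month 12 pregnancy follow-up visit a final study visit. On that reading release would come much later, but only if a pregnancy occurs and the woman joins that follow-up. This does not close the gap in general, and it leaves the trigger undefined.

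**The case against.** The strongest reply is that Section 6.3.2 sets a minimum. It bars earlier release and gives the order of events without a deadline, so a careful team could finish readings and lock the data before telling anyone. The smear procedure and the data management plan, which are referred to but not supplied, may already require this. Section 8.2.1 says positive results are shared with subjects, which suggests that smears are read during the study.

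Part of this stands. The text does not oblige release on the day of the visit, and the finding applies to this document only. But the visit is the only condition named, so release straight after it would comply. Section 6.3.2 refers to operating procedures only for unscheduled unblinding. Sharing positive results carries no timing, and cannot cover a smear taken at the final visit and not yet read.

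The reply also limits the scale, and that stands in full. A reader might infer that the blind is given up before the primary dataset exists, that the RT-PCR dataset is broadly exposed, or that the safety comparison is compromised. The documents do not support these readings. Events already recorded are fixed, RT-PCR is done on coded spots at an outside laboratory, and the primary safety window closes months earlier.

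**Conclusion.** The point holds in limited form. As written, Section 6.3.2 permits release of assignments while the last day-168 smears of symptom-free subjects are unread and while late adverse-event entries, causality revisions and queries are open. The realistic exposure is the last smear of late-finishing subjects still negative, plus those late or reopened judgements. RT-PCR exposure is low.

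The size of any bias cannot be computed, because the documents give neither turnaround times nor the distribution of finishing dates. The finding shows that unblinded readings are possible, not that they will occur. It rests on two assumptions: that no unseen plan already imposes a lock before release, and that staff in Mali could learn assignments once subjects are told. The correction is worth making because it protects a primary endpoint read by people, at very little cost.

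**What to change.** Amend Section 6.3.2 so that data stay blinded, expressly including for smear readers and for investigators who assess causality, and subjects are not told their assignment, until all of the following are met:

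- the last subject's final scheduled visit is complete;
- all smear and RT-PCR endpoint results are final;
- adverse-event grading and causality are final;
- the database is locked.

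State whether the final study visit means day 168 or the month 12 visit in Appendix C. Leave the existing provisions for unscheduled unblinding (Section 6.3.2) and for pregnancy (Section 8.4.2.3.4) unchanged.

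The cost is a protocol wording change. Subjects learn their assignment somewhat later, by the time needed for readings and lock. No visit, sample or sample-size change follows.

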6.4 STUDY INTERVENTION COMPLIANCE

Study intervention administration will be documented by study staff.

6.5 CONCOMITANT THERAPY

All concomitant prescription and nonprescription (including over-the-counter, herbal, or traditional) medications taken during study participation will be recorded. For this protocol, a prescription medication is defined as a medication that can be prescribed only by a properly authorized/licensed clinician.

Treatment with the following drugs and procedures will not be permitted unless discussed with and approved by the investigator:

- Live vaccines within 4 weeks of study agent administration.
- Killed vaccine or any COVID-19 vaccine within 2 weeks of study agent administration. (In Mali there are no standard vaccines for adults).
- Immunoglobulins and/or blood products for the duration of the study.
- Receipt of any investigational product or co-enrollment in other clinical studies of investigational products.
- Oral or IV corticosteroids at immunosuppressive doses (i.e., prednisone >10 mg/day) or immunosuppressive drugs for the duration of the study.
- Antimalarials and antibiotics with known antimalarial activity (with the exception of artemether-lumefantrine given at enrollment).

Emergent use of any drugs or blood products to treat life-threatening conditions does not require approval by the investigator and will be recorded.

7 STUDY INTERVENTION DISCONTINUATION AND PARTICIPANT DISCONTINUATION/WITHDRAWAL

7.1 DISCONTINUATION OF STUDY INTERVENTION

Study intervention may be discontinued for a protocol-defined group or arm (i.e., pausing), or it may be discontinued for all subjects and enrollment suspended (i.e., halting). Pausing and halting are described in sections [8.4.5](#) and [8.4.6](#). Subjects who have already received the study agent at the time of a pause or halt will continue planned follow-up under the protocol.

7.2 PARTICIPANT DISCONTINUATION/WITHDRAWAL FROM THE STUDY

Participants are free to withdraw from participation in the study at any time upon request. Plans for managing the involuntary withdrawal of a subject are provided in section [8.4.3](#). The reason for subject discontinuation or withdrawal from the study will be recorded on the case report form (CRF).

Subjects who withdraw after receiving study agent but prior to study completion will be encouraged to attend an early termination visit, where they will complete as many of the procedures and evaluations indicated in the schedule of activities (section [1.3](#)) as possible.

7.3 MISSED VISITS AND LOST TO FOLLOW-UP

If a participant misses 1 visit after D28 or 2 visits after D28 that are not sequential, these will not be considered protocol deviations. However, 2 missed visits in a row or a total of 3 or more missed visits (regardless of whether or not they are sequential) over the duration of the study will be considered protocol deviations.

A subject will be considered lost to follow-up if he or she fails to return for 3 consecutive scheduled visits and is unable to be contacted by the study site staff.

The following actions must be taken if a subject fails to return to the clinic for a required study visit:

- The site will attempt to contact the subject and reschedule the missed visit within 7 days, counsel the subject on the importance of maintaining the assigned visit schedule, and ascertain if the subject wishes to and/or should continue in the study. If a missed visit cannot be rescheduled, the participant may continue with the next scheduled visit.
- Before a subject is deemed lost to follow-up, the investigator or designee will make every effort to regain contact with the subject (where possible, 3 telephone calls or home visits). These contact attempts should be documented in the subject's medical record or study file.
- Should the subject continue to be unreachable, he or she will be considered to have withdrawn from the study with a primary reason of lost to follow-up.

8 STUDY ASSESSMENTS AND PROCEDURES

8.1 SCREENING PROCEDURES

Screening will be performed at all study sites. The study staff will explain the study to the prospective subject, complete the study comprehension examination and obtain consent (section [10.1](#)), and assess eligibility. Consent will be obtained before any study-related procedures are performed.

The following screening procedures and evaluations must be performed within -56 to -7 days of study intervention. Screening may take place over multiple visits if necessary.

- Confirmation of identity, age, and residency.

- Complete review of medical history and medication use.
- Complete physical examination, including height and weight.
- Vital signs (temperature, blood pressure, and pulse).
- 12-lead ECG.
- Urine collection for urinalysis (urine dipstick or formal urinalysis; acceptable laboratory parameters defined in [Appendix A](#)).
- For women, serum β -hCG pregnancy test.
- Blood collection via venipuncture for screening evaluations:
 - HIV tests: 2 rapid diagnostic tests (RDTs), plus ELISA if the RDTs are discordant. A subject will be referred for medical care for 2 positive RDTs or a positive ELISA. If the ELISA is negative, no further work-up will be done. Pre- and post-test HIV counseling will be provided.
 - HBV ELISA and HCV ELISA (PCR, if indicated) tests. If either test is positive, the subject will be referred for care regardless of the ALT result.
 - Hemoglobin typing sample will be stored at screening, and hemoglobin typing will be performed if the subject is enrolled; this test will not be used in eligibility assessments.
 - Complete blood count (CBC) with differential.
 - ALT.
 - Cr.
- Pregnancy prevention confirmation and counseling.

A prospective subject who has any clinically significant abnormal finding and/or is diagnosed with a medical condition at screening or during the conduct of the study will be notified and referred for medical care. Per national requirements for reporting communicable diseases, confirmed positive test results for HIV, HBV, and HCV will be reported to the local health department according to applicable laws and appropriate medical referrals initiated. The cost of initial and long-term treatment and care of medical conditions diagnosed during the screening process will not be reimbursed by the study but referrals to relevant specialist will be provided.

Screening evaluations may be repeated as described in section [5.5](#), at the discretion of the investigator. If screening is completed outside the specified window, all screening procedures and evaluations must be repeated.

Enrollment: If the individual is eligible and agrees to participate, he or she will be scheduled to come for an enrollment visit, as described in section [1.3](#). Enrollment is defined as the time of artemether-lumefantrine administration. A clinician will discuss the target dates and timing of the study agent administration and sample collections before completing an enrollment to help ensure that the subject can comply with the projected schedule.

8.2 EFFICACY ASSESSMENTS

8.2.1 Clinical Evaluations

The following clinical evaluations will be performed as efficacy assessments.

Medical History and Medication Review: A complete review of all medical history and medications will be conducted at screening. Subsequent visits will include a targeted review of changes in medical history or medications since the last study visit.

Physical Examination: A complete physical examination (including height and weight) will be done at screening. A targeted physical examination based on signs, reported symptoms, and medical history will be conducted at subsequent study visits. Weight will also be recorded on day 0 prior to study agent administration.

Artemether-Lumefantrine: At enrollment, all subjects will be orally administered standard artemether-lumefantrine treatment (4 tablets twice daily for 3 days) to clear any possible Pf blood-stage infection prior to study agent administration. Study investigators will provide a fat-containing drink (e.g., milk) to study participants immediately prior to administering artemether-lumefantrine to enhance its absorption, as per 2021 WHO Guidelines for Malaria.[\[25\]](#)

Randomization Procedures: Randomization for the efficacy study is described in sections [6.3.1](#) and [9.4.1](#).

Study Agent Administration and Monitoring: Study agent administration and monitoring will be performed according to the assigned arm, as described in section [6.1](#).

Illness Visit: A subject will be instructed to come in for an unscheduled visit if he or she has symptoms of malaria or other symptoms. The subject will be evaluated by the study team and referred for standard care according to local guidelines. At an illness visit, the subject may undergo review of medical history and concomitant medications, a focused physical exam for symptoms of malaria or other diseases, vital sign measurement, and a fingerprick or venipuncture blood collection for blood smear for malaria diagnosis as well as a dried blood spot for Pf RT-PCR for research purposes.

Malaria Diagnosis and Management: If a subject has a malarial infection, we will share these results with the subject and provide standard treatment in accordance with the recommendations of the Mali National Malaria Control Program. According to the national guidelines, asymptomatic malarial infections in adults are not treated. Malaria treatment is given only when symptoms are present along with positive blood smear results. RT-PCR is not commonly used for routine malaria diagnosis.

